1.1 Study Aims

1.1.1 Primary Aim 1

Determine the feasibility and acceptability of the Blueprint app.

1.1.2 Primary Aim 2

Determine the clinical impact on ICU survivors' 1 and 3 month psychological distress symptoms of intervention groups compared to usual care control.

1.2 Study Hypotheses

1.2.1 Primary Hypothesis 1

The primary hypothesis is that the mobile CST app 'Blueprint' will be feasible and acceptable based on comparison of observed to a priori benchmarks.

1.2.2 Primary Hypothesis 2

The secondary hypothesis is, compared to usual care, the intervention participants will have improvement in symptoms of psychological distress (HADS and PTSS scores) at the 1 and 3 month timepoints (T2 and T3).

2 Study Design and Study Population

Participants are patients who were admitted to the ICU and were critically ill with either respiratory failure/insufficiency or cardiac failure/insufficiency. Additionally, participants experienced a high level of distress (HADS ≥ 8) at baseline.

This is a randomized clinical trial, where participants are consented and randomized to 1 of 3 arms (2 intervention arms, 1 control arm) in a 1:1:1 ratio. A total randomized sample size of 45 participants (15 per arm) was targeted. A method of minimization was used for randomization, with the aim to balance 3 stratification characteristics: ICU service (medical, surgical), baseline HADS score (<14 , ≥ 14), and age (<50 , ≥ 50).

2.1 Inclusion Criteria

Patients included in Blueprint satisfied the following inclusion criteria:

At time of hospital admission:

- Age ≥ 18 years
- Managed in an adult ICU, step-down unit, or specialized care unit for ≥ 24 hours during the time in which inclusion criterion #3 is met.
- Presence of acute cardiac or respiratory failure, defined as having ≥ 1 of the following:
 - Acute respiratory failure / insufficiency, defined as ≥ 1 of the following:
 - Mechanical ventilation via endotracheal tube for ≥ 4 hours
 - Non-invasive ventilation (CPAP, BiPAP) for ≥ 4 hours in a 24-hour period provided for acute respiratory failure in an ICU (not for obstructive sleep apnea or other stable use)
 - High flow / opti-flow nasal cannula or face mask oxygen use
 - $\geq 25\%$ increase in baseline nasal cannula rate
 - Acute cardiac failure / insufficiency, defined as ≥ 1 of the following:
 - use of vasopressors for shock of any etiology
 - use of inotropes for shock of any etiology
 - use of pulmonary vasodilators
 - use of aortic balloon pump or cardiac assist device for cardiogenic shock
 - use of diuretic intravenous drip
- Cognitive status intact, defined as:
 - No history of significant cognitive impairment (e.g., dementia)
 - Absence of current, significant cognitive impairment (≥ 3 errors on the Callahan cognitive status screen)
 - Decisional capacity present
- Absence of severe and/or persistent serious mental illness that could disrupt study participation, as noted in the electronic medical record (EMR) or affirmed by clinical staff at the time of screening and approach for consent. Defined as any of the following:

- Treatment for severe or unstable mental illness (e.g., psychosis, schizophrenia) within the last 6 months preceding the current hospital admission
- Active substance abuse that impairs ability to participate
- Endorsing suicidality at time of admission or informed consent discussion
- English fluency.

At time of discharge:

- Elevated baseline psychological distress symptoms, defined as HADS total score of ≥ 8 at the completion of survey 1, T1.

2.2 Exclusion Criteria

Patients were excluded from Blueprint if they satisfied the following exclusion criteria:

At time of hospital admission:

- Complex medical care expected soon after discharge (e.g., planned surgeries, transplantation evaluation, extensive travel needs for follow up care, disruptive chemotherapy/radiation regimen)
- Unable to complete study procedures as determined by staff.
- Lack of access to either reliable smartphone with cellular data plan or wifi

At time of hospital discharge:

- Failure to randomize within 1 month after discharge from the hospital to home.
- Failure to access app within 1 month after randomization.

The following additional exclusion criteria were applied after data collection:

- Any data recorded after a participant has withdrawn

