#### **4. Study Objectives, Hypotheses, and Outcomes**

The overall objective of the pilot RCT is to determine the feasibility, acceptability and clinical impact of the intervention on patients' 1- and 3-month psychological distress symptoms of a self-directed mobile coping skills training (mCST) intervention, known as "Blueprint" as compared to usual care control.

The primary hypothesis in which this study is based is that the mCST will be feasible and acceptable based on comparison of observed to priori benchmarks.

The second hypothesis is compared to usual care, the mCST use by enrolled subjects will lead to improvement in symptoms of psychological distress via the HADS and PTSS at the 1- and 3-month mark post randomization.

The primary outcome of the pilot RCT is centered on acceptability and feasibility. The Client Satisfaction Questionnaire 8 will measure acceptability with open-ended participant feedback completed at the time of T3, which is considered end of study (EOS). Feasibility will be measured by frequency of randomization, retention, and adherence. Secondary outcomes are HADS and PTSS scores at 1 and 3 months post-randomization.

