3.1 Primary Outcome(s)

Variable	Dataset	Description	Specifications

hads	Blueprint/Baseline	HADS total score at T0	Continuous
Hads	Blueprint/T1	HADS total score at T1	Continuous (may need to be derived from item scores HADS01—HADS14)
Score_hads	Blueprint/T2	HADS total score at T2	Continuous (may need to be derived from item scores HADS01—HADS14)
Score_hads	Blueprint/T3	HADS total score at T3	Continuous (may need to be derived from item scores HADS01—HADS14)
ptss	Blueprint/T1	PTSS total score at T1	Continuous (may need to be derived from item scores ptss_1—ptss_10)
Score_ptss	Blueprint/T2	PTSS total score at T2	Continuous (may need to be derived from item scores ptss_1—ptss_10)
Score_ptss	Blueprint/T3	PTSS total score at T3	Continuous (may need to be derived from item scores ptss_1—ptss_10)
D3mo_HADS	Blueprint/T3 Blueprint/T1	Change in HADS at 3 months	Derived as Score_hads(T3) - ???
D1mo_HADS	Blueprint/T2 Blueprint/T1	Change in HADS at 1 months	Derived as Score_hads(T2) - ???
D3mo_PTSS	Blueprint/T3 Blueprint/T1	Change in PTSS at 3 months	Derived as Score_ptss(T3) - ???
D1mo_PTSS	Blueprint/T2 Blueprint/T1	Change in PTSS at 1 months	Derived as Score_ptss(T2) - ???
ADLs/IADLs	T1, t2, t3		Not really an outcome but...
Systems Usability Scale	T1		
PHQ-10 physical symptom scale	T1, t2, t3		
Quality of life 100-point VAS	T1, t2, t3		
List		Feasibility	
Eligibility: 70% of positive screens Consent: 80% of eligible Randomized: 80% of consented Retention: 80% Adherence: 75% of tasks
 
***note that these need to be defined a bit more specifically

CSQ-8	`	Acceptability	

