3.2 Primary Exposure(s)

Variable	Dataset	Description	Specifications
Plan_name	Blueprint/Participants	Trial Arm	
A multi-level categorical variable
 
- Blueprint Screening & Baseline: Exclude- Blueprint (Group 1): Arm 1- Blueprint (Group 2): Arm 2- Blueprint (Control): Arm 3

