3.3 Other Variables of interest

Variable	Dataset	Description	Specifications

4 Statistical Analysis Plan

All analyses will be done using SAS 9.4. Continuous variables will be summarized with mean/standard deviation/median/Q1-Q3/range and categorical variables with frequency counts and percentages. Number of missing data for each variable will be reported.

4.1 Analysis Plan for Primary Aim 1

1. First, we will describe our cohort. In Table 1 we will summarize participant characteristics overall and by arm. No statistical tests will be provided as this was a randomized trial, and ideally groups should be balanced.
2. To assess Aim 1 for feasibility and acceptability we will evaluate CSQ-8 and SUS scores. Results will be reported in Table 2.

4.2 Analysis Plan for Primary Aim 2

1. To address Aim 2, we will describe the secondary outcomes at each time point by arm, as well as the change in scores at T2 and T3 from T1 in Table 3. Any additional secondary outcomes will be described in this table.
2. To assess if there was change at each timepoint of interest between the arms we estimate mean changes (and 95% CI) from baseline to each timepoint for each distress outcome (HADS, PTSS) using a general linear model (PROC MIXED). Model parameters will include treatment arm (1, 2, 3), time indicator (T1, T2, T3), and an arm by time interaction term. Change estimates and CI's will be reported in Table 4. To quantify clinically important differences, rather than report p-values which is not recommended for pilot studies with

small sample sizes, we will compare the estimated group mean differences and 95% CI's to half (0.5) of the baseline standard deviation (SD) of each outcome score.

5 Appendix I: Planned figures and tables

Figure 1: CONSORT Diagram

Table 1: Demographic characteristics of participants at baseline

Characteristic	Arm 1: Intervention Group 1 (Blueprint + Therapist) N=	Arm 2: Intervention Group 2 (Blueprint only) N=	Arm 3: Control (Usual Care) N=	Total N=
Stratification Variables				
Age				
<50				
≥50				
ICU Service				
Medical				
Surgical				
Baseline HADS				
<14				
≥14				
Other Baseline Characteristics				
Age				
Mean (sd)				
Median				
Q1, Q3				
Range				
Gender				
Male				
Female				

Table 2: Feasibility and Acceptability

Characteristic	Arm 1: Intervention Group 1	Arm 2: Intervention Group 2	Arm 3: Control (Usual Care)	Total N=

	(Blueprint + Blueprint Therapist) N=		N=
	N=	N=	
Feasibility			
% Consented	--	--	--

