% Randomized	--	--	--
% Retained			
% Completed Surveys			
T1			
T2			
T3			
All timepoints			
% Completed all intervention components		--	--
Acceptability			
CSQ Score			

Table 3: Participant Outcomes

Characteristic	Arm 1:	Arm 2:	Intervention Arm 3: Group 1 (Blueprint + Blueprint Therapist) N=	Control (Usual Care) N=	Total N=
	Intervention	Intervention			
	Group 1 (Blueprint + Blueprint Therapist) N=	Group 2 (Blueprint only) N=			
Hospital LOS (Discharge - admission)					
Hospital discharge disposition					
3 month disposition					

Table 4: Observed and Estimated mean score and differences by Arm and Time for HADS and PTSS outcomes

	Baseline (T1?)	1 Month (T2)	3 Months (T3)	Δ 1 month - Baseline	Δ 3 months- Baseline
HADS					
Observed Score					
Arm 1 (BP + Therapist)					
Arm 2 (BP only)					
Arm 3 (Control)					
Estimated Mean Score (95% CI)					
Arm 1 (BP + Therapist)					
Arm 2 (BP only)					

Arm 3 (Control)					
Diff (Arm 1 - Arm 3)					
Diff (Arm 2 - Arm 3)					
PTSS					
Observed Score					
Arm 1 (BP + Therapist)					
Arm 2 (BP only)					
Arm 3 (Control)					
Estimated Mean Score (95% CI)					
Arm 1 (BP + Therapist)					
Arm 2 (BP only)					
Arm 3 (Control)					
Diff (Arm 1 - Arm 3)					
Diff (Arm 2 - Arm 3)

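### Both documents exclude patients who do not access the app in the month after randomisation; applied as written, this would remove app-arm non-users from primary feasibility measures and the arm comparison

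*SAP*

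**What the plan says.** Protocol section 5 (exclusions at discharge) and SAP section 2.2 carry the same item: "Failure to access app within 1 month after randomization". The SAP introduces its list with "Patients were excluded from Blueprint if they satisfied the following exclusion criteria".

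The protocol gives eligibility a continuing role. In section 7, randomised status is defined by still meeting all the section 5 criteria, and under Study Visits both T2 and T3 are scheduled only for patients who are still eligible.

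The outcomes concerned are primary. Protocol section 4 states: "Feasibility will be measured by frequency of randomization, retention, and adherence". SAP section 3.1 sets the benchmarks as "Retention: 80% Adherence: 75% of tasks", gives no denominator for either, and adds "note that these need to be defined a bit more specifically". Protocol section 9 tests the benchmarks among those who received the app, without defining a recipient.

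For the arm comparison, SAP section 3.2 maps app plans to arms (for example "Blueprint (Control): Arm 3") with no filter on access. SAP section 4.2 says "Model parameters will include treatment arm (1, 2, 3), time indicator (T1, T2, T3), and an arm by time interaction term". Neither document names an all-randomised or intention-to-treat set.

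**The concern.** An eligibility criterion should be decidable before allocation. This one is decided up to a month afterwards, and it depends on behaviour that the trial exists to measure. In a pilot of a self-directed app, never opening it is a central feasibility failure. The course lasts 28 days (Protocol section 3), so a patient who does not use the app in the month after randomisation has done none of it within the course.

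If such patients are treated as excluded, adherence is computed among people selected for having used the app. Retention may be flattered in the same way. The HADS and PTSS contrast would also lose patients after randomisation. That loss could fall on the app arms alone, since usual care has no coping skills app to open. A CONSORT diagram would probably show the loss but would not correct the percentages. A later definitive trial would then be planned on figures that leave out the patients hardest to engage.

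**Working it through.** **Does any passage settle the matter?** For removal: the exclusion item in both documents, the SAP sentence saying that patients meeting it were excluded, and the protocol's tie between continued eligibility and T2/T3. Against removal:

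- Protocol section 3 has staff remind patients who stop responding.
- Protocol section 7 handles non-compliance through loss to follow-up or withdrawal, with those patients kept on the enrolment log.
- SAP section 2.2 has a separate list of exclusions made after data collection. Its only item is data recorded after withdrawal.
- In SAP section 3.2 the only plan marked for exclusion is the screening and baseline plan.

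None of these says that a patient meeting the exclusion stays in follow-up or analysis. The rule is neither confirmed as an analysis filter nor overridden.

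**What counts as access?** It is undefined. T1 is completed in the app (Protocol section 7), and a closing T1 screen confirms enrolment (Protocol Appendix 3). If that session counts, the rule removes almost nobody.

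**Inputs.** The benchmarks (80% and 75%) are set, not derived, so there is no plan calculation to reproduce. App-arm sizes are 2 × 15 = 30 (SAP section 2) and 25 + 25 = 50 (Protocol section 2). No non-access rate is given, so every rate below is an assumption.

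**Adherence as mean share of tasks.** Let *a* be the share completed by openers and *f* the proportion who never open the app, counted as 0%. Over all randomised app patients, adherence = (1 − *f*) × *a*. After exclusion it is *a*. The overstatement is *f* × *a*, which is never negative and is positive whenever anyone is removed and others did any tasks.

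| *f* (assumed) | All randomised, *a* = 85% | After exclusion |
|---|---|---|
| 0% | 85.0% | 85% |
| 5% | 80.8% | 85% |
| 10% | 76.5% | 85% |
| 20% | 68.0% | 85% |

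The all-randomised figure falls below 75% when *f* > 1 − 0.75/*a*. That is 6.3% for *a* = 80%, 11.8% for *a* = 85% and 16.7% for *a* = 90%.

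**Retention.** With *r* retained of *n*, and *k* non-users removed who were all lost, *r*/*n* becomes *r*/(*n* − *k*). The point estimate crosses 80% only when 0.8(*n* − *k*) ≤ *r* < 0.8*n*.

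- *n* = 30, *k* = 1: 23.2 ≤ *r* < 24, so no whole number crosses.
- *n* = 30, *k* = 3: 21.6 ≤ *r* < 24, so *r* = 22 or 23. For example, 22/30 = 73.3% becomes 22/27 = 81.5%.
- *n* = 50, *k* = 5: 36 ≤ *r* < 40. For example, 36/50 = 72.0% becomes 36/45 = 80.0%.
- If the removed patients had been retained, the figure falls: 24/30 = 80.0% becomes 22/28 = 78.6%.

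**The same retention figures under the protocol's chi-square test against 80%.**

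- 22/30: expected 24 and 6; 4/24 + 4/6 = 0.833, p = 0.36.
- 22/27: expected 21.6 and 5.4; 0.16/21.6 + 0.16/5.4 = 0.037, p = 0.85.
- 36/50: expected 40 and 10; 16/40 + 16/10 = 2.0, p = 0.16.
- 36/45: observed equals expected, p = 1.0.

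None differs from the benchmark at 5%, before or after removal. The adherence cases cannot be tested this way without a standard deviation. The effect on HADS and PTSS cannot be sized, and may be small because many non-users would have no T2 or T3 scores.

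**The case against.** The best defence is that this is a misplaced eligibility item and not an analysis rule. The SAP keeps a separate list for exclusions made after data collection, and non-access is not on it. Arms are mapped and modelled without an access filter. The earlier feasibility benchmarks run as a cascade (of positive screens, of eligible, of consented), so those randomised would be the natural next denominator for retention. All of this stands as evidence that removal may not be intended. It does not settle the point, because the after-collection list is described as additional to the criteria above it and the retention denominator is never stated.

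Three stronger readings are tempting and are not supported. A reader might infer that the plan says non-users leave the percentages; no passage says so. A reader might infer that exclusion is the only provision for them; the protocol also has reminders, loss to follow-up and withdrawal. A reader might infer that the rule would reverse the retention verdict; that assumes a point-estimate pass mark, whereas the protocol specifies tests, under which the retention examples above do not change.

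It is also fair to object that counting non-access as 0% presumes an adherence window. Protocol section 10 allows app use between T2 and T3, so a late starter could complete tasks after the first month. The window has to be stated.

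**Conclusion.** The concern holds as a gap between a post-randomisation exclusion and an undefined analysis set. Applied as written, the rule would remove app-arm non-users. For mean adherence the direction is certain: removal cannot lower it. For retention it depends on whether those patients are also lost. The randomised comparison of HADS and PTSS would no longer be fully as randomised.

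The size is unknown. It runs from near nil, if the T1 session counts as access, to 8.5 percentage points of adherence at 10% non-openers (85 − 76.5) and 17 points at 20% (85 − 68.0). These figures assume that openers complete 85% of tasks. The retention examples cross 80% as point estimates only. Confidence is medium, because the documents give neither a non-access rate nor a definition of access. The item should be fixed.

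**What to change.** - Delete the item from both exclusion lists, or state in both documents that it removes no randomised patient from follow-up or analysis.
- Define access as app use after randomisation, separate from the T1 session, and report non-access by arm as a feasibility outcome.
- Compute adherence over all patients randomised to Arms 1 and 2 within a stated window (the 28-day course), counting no use in that window as 0% of tasks.
- Compute retention over all randomised patients, by arm, and for Arms 1 and 2 combined where it is compared with the benchmark.
- Analyse HADS and PTSS by assigned arm with all available data. Keep a users-only analysis as a labelled sensitivity analysis.

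The cost is SAP wording and a short protocol amendment. No new usage data are needed, because the app dashboard already tracks individual use (Protocol section 3). The feasibility percentages may look less favourable. If data collection has ended, only T2 and T3 data already held can be restored.

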  - A native app that uses this downloaded as a self-contained program and is subject to the device operating system. The mCST created for this study known as "Blueprint", was developed, and is maintained by Pattern Health ([name]).
- Patient Health Questionnaire-10 (PHQ-10)
  - Physical symptoms
- Post-Traumatic Stress Scale survey (PTSS)
  - PTSD symptoms

- **Protocol Deviation (PD)**
  - An inadvertent event or event this is out of the control of the study team and/or the subject that occurs outside of the study protocol design and/or procedures.
- **Protocol Violation**
  - An act of intentionality that is committed by the study team and/or the subject that occurs outside of the study protocol design and/or procedures.
- **Serious Adverse Event (SAE)**
  - Defined as an adverse event that is both serious and expected in nature; the event may have a reasonable possibility that it is related to a study. SAEs for this study are defined as a suicide attempt, a hospitalization, or death.
- **Suicide Ideation (SI)**
  - The idea of committing self-harm and/or the intent to act on the idea of committing self-harm.
- **Unanticipated Problem (UP)**
  - Any other event, not meeting the definition of PD, UP, AE or SAE that, in the opinion of the principal investigator, merits documentation as it occurred outside the expected design of the study and/or study procedures. These events, like PDs, UPs, AEs, or SAEs, may be reported to the IRB and/or the study sponsor, as applicable.

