- **Withdraw by PI or Self:** defined as any individual who voluntarily consents to participate in the study, but is then withdrawn from the study. The PI may withdraw a participant at any time without their consent if the PI deems it is in their best interest to no longer participate OR the patient demonstrates continuous lack of compliance with study protocol and study procedures. Additionally, if the patient is re-admitted to the hospital during the time of randomization, he/she will be withdrawn from the study by the PI. The study team may re-enroll the patient at the time of discharge following the same screening procedures. The patient may withdraw themselves at any time; the study team will be asked to document the reason for withdraw for study records. Patients who reach this status have no additional follow-ups or study requirements. Patients who are assigned this status must be maintained on the enrollment log.
- **Lost to Follow-Up (LTF):** defined as any individual who voluntarily consents to participate in the study but after non-compliance and at least 3 documented, attempted contacts appropriately spaced 1-5 days apart, the individual will be considered LTF.
  - For aim 2 only:
    - Patients who reach this status have no additional follow-ups or study requirements. Patients who are assigned this status must be maintained on the enrollment log.
    - A patient who returns the study team's contacts within 1 week of last attempted contact may resume study participation.
- **Completed:** defined as any individual who both consented and randomized to the study and completed T1-T3 (aim 2 only) or any individual who completed assigned study visit (aim 1 only). Individuals who reach this status have no additional follow-up or study requirements. Individuals who are assigned this status must be maintained on the enrollment log.

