### Suicidality Response Plan

Should a patient indicate to a study team member, thoughts of suicidality or ideation of suicidality, the Suicidality Response Plan could be activated.

If the participant is deemed to be at high risk based on direct interaction plus the C-SSRS item response, the delegated study team member will administer the C-SSRS to assess the participant to determine if they endorse active suicidal ideation. The trained staff will also determine if the participant is currently being treated by a mental health professional.

If the patient is deemed not to be actively suicidal, they will be given a list of local mental health resources as follows:

- Duke: Call Emergency Psychiatry at [contact] or [contact], available 24 hours a day, 7 days a week.
- The National Suicide Prevention Lifeline - [name] is a free, 24-hour hotline available to anyone in suicidal crisis or emotional distress.

If the participant is considered actively *suicidal* then at least one of the following plans will be followed depending on the location of the participant for each of the following situations:

- Situation 1
  - If the participant is with one of the study personnel, the study personnel will notify the site PI one of the other PIs immediately.
  - The study personnel will either physically walk the subject to the emergency department, or call a Psychiatric Emergency services number relevant to the site as described above.
- Situation 2
  - If the participant is on the telephone:
    - The study personnel will notify the site PI one of the other PIs immediately
    - The study personnel will stay on the telephone with the subject participant.
    - The study personnel will immediately contact 911 to initiate an on-site rescue if such action is clinically indicated.

- The study personnel will stay on the telephone with the subject until EMS services have contacted the participant.

If the participant is determined to be actively suicidal and require immediate medical therapy, they will be withdrawn from the study.

As described above, all concerns about participant safety will be discussed immediately with the PI - including concerning severe distress that does not involve suicidality.

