For these situations, once an “alert situation” is known, the PI will refer the participant if needed (based on a PI-led phone call) to local psychological resources. The study team will also make urgent and emergency referrals as needed based on information learned.

To date based on some studies that have included over 400 participants, we have found that <5% of participants will require a call from the PI during some point in the study period. Of those, none has required referral to acute psychiatric care after a detailed interview from the PI. After a disposition / solution has been made, both the resolution (and follow up) will be documented in the ‘contact log’ section of the data system for reporting to the DSMB.

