#### Period and Frequency for Event Assessment and Follow-Up

Protocol deviations and other unanticipated problems, as well as AEs and SAEs, will be recorded in the data collection system throughout the study and reported, as appropriate, to the IRB, study sponsor, and/or DSMB, when applicable.

The study team will record all reportable events with start dates occurring any time after informed consent is obtained until 7 (for non-serious AEs) or 30 days (for SAEs) after the last day of study participation. At each study visit, the study team will inquire by way of verbal or written request and/or EMR review, of the occurrence of AE/SAEs since the last visit. Events will be followed for outcome information until resolution or stabilization.

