## Appendix 1: Schedule of Events

	Day 0 (In-Hospital, Baseline)	Day 1 , T1 (Discharge) (+30 days)	Week 1	Week 2	Week 3	Week 4 Day 30, T2 (+60 days)	Day 90 (+30 days), T3
Screening*	X						
Consent (a)*	X						
App Registration*	X						
Baseline Survey (b)*	X						
Usability Survey*							
T1 Survey (c)		X					
T2 Survey (c)						X	
T3 Survey (c)							X
Weekly Check-In (d)			X	X	X		
Progressive Muscle Relaxation and Pleasant Imagery (mCST)			X				
Pleasant Activities and Activity Rest Cycling				X			
Fast Relax and Managing Negative Thoughts						X	
Problem Solving and Maintenance							X
Data Entry (e)	X	X				X	X
AE/SAE assessment (f)	X	X				X	X
Survival Status (f)		X				X	X
End of Study (g)							X

- a) Patients may be approached and consented during their admission, if well enough; their hospitalization (e.g., while in step-down), or within 1-3 days of returning to their home for participation in the study
- b) Completion of the baseline survey includes the patient providing self-reported information such as social and demographic information and general health status.
- c) Surveys 1, 2 and 3 will be completed via the app by all study participants, regardless of arm assignments. Patients who are assigned to the control arm will be alerted when it is time to complete their T2 and T3 via app notification.
- d) For those participants assigned to Arm 1 or 2, they will complete a weekly check-in to ascertain overall safety of the patient and usefulness of coping skills practice.
- e) AE/SAE assessment and survival status will be completed via EMR review and/or telephone interview.
- f) Study completion for patients enrolled in the study is considered to occur at the completion of T3. However, participants may undergo EOS if they are withdrawn from the study by the PI or opt to withdraw from the study voluntarily at any time. Should withdraw of a patient occur, the reason for withdraw and date of withdraw will be documented. AE/SAEs and survival status will be noted, as applicable.

\*For aim 1 only.

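### SAP 2.2 discards all data recorded after withdrawal with no exception for safety or survival data, although the protocol goes on recording SAEs for 30 days

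*SAP*

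**What the plan says.** SAP 2.2 ends with one additional exclusion, applied once data have been collected: "Any data recorded after a participant has withdrawn". Neither document narrows it to questionnaires or app use.

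The protocol defines the safety data broadly enough for the rule to matter. Under Abbreviations and Definitions, "SAEs for this study are defined as a suicide attempt, a hospitalization, or death". Under Period and Frequency for Event Assessment and Follow-Up, reportable events are recorded from consent "until 7 (for non-serious AEs) or 30 days (for SAEs) after the last day of study participation". The notes to the Schedule of Events (Appendix 1) add that when a patient is withdrawn, "AE/SAEs and survival status will be noted, as applicable".

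Two withdrawals are triggered by safety events. The Suicidality Response Plan states: "If the participant is determined to be actively suicidal and require immediate medical therapy, they will be withdrawn from the study". The participant statuses under Screening, Recruitment and Consent state that "if the patient is re-admitted to the hospital during the time of randomization, he/she will be withdrawn from the study by the PI". The same status entry says: "Patients who reach this status have no additional follow-ups or study requirements".

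On the output side, no variable in SAP section 3 and no table in Appendix I names an AE, an SAE or death. Table 3 has a by-arm row for three-month disposition, with no categories given.

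**The concern.** The protocol requires certain records and the SAP, taken at its word, removes them from the analysis data. The removal is not random across patients. Some withdrawals follow an SAE or a suicidal crisis, and in those patients a later death or SAE is a particular concern. The trial is a pilot meant to inform a definitive RCT, so its reported account of deaths should match what the protocol collected. As written, a death after withdrawal could be on file and reported to the sponsor, yet be missing from the by-arm table.

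**Working it through.** The plan attaches no figure to this rule, so there is nothing to reproduce. The check sets the provisions side by side and then gauges the scale.

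**1. Does the rule reach safety data?** Take the day of withdrawal as the last day of participation. This is an assumption, because the protocol does not equate the two. The 30-day SAE window then lies wholly after withdrawal, and SAP 2.2 excludes all of it. The triggering event normally precedes withdrawal and is kept. It could be lost only if entered late, because the SAP does not say whether event date or entry date governs.

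**2. How much of the recording window is that?** For withdrawal on day d after randomisation, the window runs to day d + 30 and the excluded share is 30/(d + 30):

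- d = 10: 30/40 = 75%
- d = 30: 30/60 = 50%
- d = 60: 30/90 = 33%

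These are shares of days, not of events.

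**3. Which planned output changes?** Only three-month disposition, and only if that row is meant to count deaths. SAP section 4 says that missing counts will be given for every variable, so excluding the record makes the patient missing. It does not make the patient event-free. Suppose one death in an arm is recorded after withdrawal. Intervals are exact (Clopper-Pearson) 95%; with zero events the upper limit is 1 − 0.025^(1/n).

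| Arm size (source) | Death kept | Death excluded |
|---|---|---|
| 10 (protocol, control) | 1/10 = 10.0% (0.3 to 44.5%) | 0/9, 1 missing (0 to 33.6%) |
| 15 (SAP, each arm) | 1/15 = 6.7% (0.2 to 31.9%) | 0/14, 1 missing (0 to 23.2%) |
| 25 (protocol, each app arm) | 1/25 = 4.0% (0.1 to 20.4%) | 0/24, 1 missing (0 to 14.2%) |

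Both sets of arm sizes are shown because the SAP targets 45 patients (15 per arm) and the protocol 60 (25, 25 and 10).

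**4. How many patients could be affected?** For suicidality, the protocol cites over 400 earlier participants, of whom fewer than 5% needed a call from the PI, and of those "none has required referral to acute psychiatric care after a detailed interview from the PI". Taking referral as a proxy for the withdrawal trigger, 0/400 has an exact 95% upper limit of 0.92%. That is 0.0092 × 45 = 0.41 patients, or 0.0092 × 60 = 0.55.

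The documents give no rate for readmission or death. As an assumption only, let 5 to 20% of patients be withdrawn for safety (w) and 5 to 20% of those have a later recorded death or SAE (p). The expected number dropped is N × w × p:

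- N = 45: 45 × 0.05 × 0.05 = 0.11, up to 45 × 0.20 × 0.20 = 1.8
- N = 60: 60 × 0.05 × 0.05 = 0.15, up to 60 × 0.20 × 0.20 = 2.4

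The chance of dropping at least one, 1 − (1 − wp)^N, runs from 11% to 84% for N = 45 and from 14% to 91% for N = 60. The width of these ranges shows how little the documents settle.

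**The case against.** The strongest reply is that little is at stake. Withdrawn patients have no further follow-up. Events are asked about at study visits, and the medical-record check for death is tied to T2 and T3, so few post-withdrawal events may ever be collected. The readmission trigger is ambiguous: with re-enrolment at discharge through the same screening procedures, it may mean readmission around T1 only. The T2 and T3 surveys ask about readmission, which suggests that some readmitted patients stay in. Oversight does not run through the SAP: deaths go to NHLBI and the DSMB Chair within 72 hours, other SAEs are summarised quarterly, and the DSMB reviews adverse events. All of this stands, and it limits the size of the problem. It does not justify discarding what the protocol does collect.

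A reader might also infer three stronger things, and the documents support none of them:

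- That the rule hides SAEs in general. It does not, because the SAP plans no by-arm AE or SAE output, so non-fatal SAEs are absent for every patient, withdrawn or not.
- That an arm with a death would appear event-free at full size. It would not, because the patient becomes missing and the missing count is reported.
- That the comparison between arms is biased. The rule is the same in every arm, and nothing in the documents shows that safety withdrawals differ by arm.

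**Conclusion.** The point holds in a limited form. SAP 2.2 is unqualified and conflicts with the protocol's SAE window and with its instruction to note events and survival status at withdrawal. The direct consequence is that a death recorded after withdrawal goes missing from one row, assuming that row counts deaths and that withdrawal ends participation. With 15 per arm, that is 0/14 with one missing in place of 1/15. The indirect consequence is that any SAE count produced later would omit post-withdrawal events unless the rule is changed first. The number of patients is unknown and probably small. HADS, PTSS and feasibility results do not depend on an exception for safety data, and reporting to the DSMB and NHLBI is untouched. This is a worthwhile, inexpensive improvement and not a threat to the trial's main results.

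**What to change.** 1. Limit the SAP 2.2 exclusion to survey and app-use data. State that AE, SAE and survival data collected within the protocol's reporting window are kept, unless the participant withdrew consent to record review.
2. Define three-month disposition for all randomised patients as dead, in hospital, home or unknown.
3. List the defined AEs, SAEs and deaths descriptively by assigned arm, without tests, noting that withdrawn patients have a shorter observation window.

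The cost is a little analyst time to link the AE/SAE records: SAP 2.3 names an app export and a REDCap file and describes neither as holding them. No new visits are needed. The change cannot recover events that were never collected. A patient withdrawn on day 10 has an SAE window ending on day 40 (10 + 30), so some withdrawn patients will still be classed as unknown at three months.
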